3.11. Visit Windows

It is expected that all visits should occur according to the protocol schedule. In data listings, the relative day of all dates will be presented.

The efficacy time frame for histopathologic regression and virologic clearance is defined as any time starting from 14 days before the protocol-specified visit week.

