1.1.3. Study Objectives

1.1.5.1. Primary Objectives

The primary objective is to determine the efficacy of 3 doses of VGX-3100 with respect to combined histopathologic regression of anal or anal/peri-anal HSIL and virologic clearance of HPV-16 and/or HPV-18.

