1.2. Study Design

1.2.1. Synopsis of Study Design

HPV-203 is a Phase 2, open-label efficacy study of VGX-3100 (DNA plasmids encoding E6 and E7 proteins of HPV types 16 and 18) administered by IM injection followed by EP in adult men and women who are HIV negative with histologically confirmed anal or anal/peri-anal

HSIL associated with HPV-16 and/or HPV-18. Approximately 24 subjects will receive at least 3 doses of VGX-3100. Each dose of VGX-3100 will be administered IM in a 1-mL volume followed immediately by EP.

To be eligible for the study, subjects must consent to participate and agree to the collection of anal lesion tissue samples for anal cytology and genotyping, a Digital Anal Rectal Examination (DARE), blood samples for immunologic assessments, high-resolution anoscopy (HRA) and HRA-guided biopsies. All intra-anal and/or peri-anal lesion(s) of adequate size ($\geq 4\text{mm}$) will be biopsied at Screening. Biopsy slides will be sent to a Pathology Adjudication Committee (PAC) for evaluation before enrollment. To be eligible for enrollment, the PAC must assign the diagnosis of anal or anal/peri-anal HSIL (AIN2, AIN3, PAIN2, PAIN3) based on the biopsy sample(s). Subjects must also have intra-anal and/or peri-anal lesion tissue test positive for HPV genotype 16 and/or 18 to be eligible for participation in the study.

Depending upon their disposition with regard to histologic and lesion area changes during the trial, all eligible subjects who consent to participate in the HPV-203 study will receive at least three doses of VGX-3100 (6 mg in 1 mL) administered IM (deltoid, preferred site, or anterolateral quadriceps, alternate site), each followed immediately by EP with the CELLECTRA™ 5PSP device. The first study treatment will be administered on Day 0, the second at Week 4, and the third at Week 12. Partial response to VGX-3100 may still be of medical importance by being able to limit the extent of surgery necessary. For partial responders at Week 36, a fourth dose may be administered at Week 40.

To assess quality of life and related impacts on subjects, PRO instruments will be provided and will include the Short Form Health Survey version 2 (SF-36v2™), the EQ-5D-5L, and 2 additional PRO questions assessing quality of life after surgery or biopsy.

The total duration of the study is up to 10 weeks for the screening period and up to 88 weeks for the treatment and follow-up periods.

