4.3.1. Primary Efficacy Endpoint

The primary endpoint is the combined response outcome of histologic regression of anal or anal/perianal HSIL and virologic clearance of HPV-16/18 in intra-anal and/or peri-anal lesion tissue at Week 36. Histologic regression is defined as no evidence of anal or anal/peri-anal HSIL on histology. Virologic clearance is defined as no evidence of HPV-16 and/or HPV-18 from intra-anal and/or peri-anal tissue by type-specific HPV testing. A treatment responder is defined as a subject with no histologic evidence of anal or anal/peri-anal HSIL and no evidence of HPV-16 or HPV-18 in anal lesion tissue and who did not receive any non-study treatment of curative intent of intra-anal and/or peri-anal lesions. A treatment non-responder is defined as a subject with histologic evidence of anal or anal/peri-anal HSIL, adenocarcinoma-in-situ, or anal or anal/peri-anal carcinoma, a subject with evidence of HPV-16/18 in anal lesion tissue, or a subject who received non-study treatment of curative intent of intra-anal and/or peri-anal lesions.

Table 2: Definition of Responder and Non-Responder for Primary Endpoint

Responder	Non-Responder

 • No histologic evidence of anal or anal/peri-anal HSIL in qualifying or new lesions AND • Negative PCR for HPV-16 or HPV-18 in anal lesion tissue in qualifying or new lesions AND • No non-study treatment of curative intent of intra-anal and/or peri-anal lesions 	
 • Histologic evidence of anal or anal/peri-anal HSIL, anal adenocarcinoma-in-situ, anal or anal/peri-anal carcinoma in qualifying or new lesions OR • PCR positive for HPV-16 or HPV-18 in anal lesion tissue in qualifying or new lesions OR • Any non-study treatment of curative intent of intra-anal and/or peri-anal lesions

Note: The efficacy time frame is defined by samples obtained any time starting from 14 days before the protocol-specified target date of Week 36. The first such sample determines the histology endpoint. The most recent HPV clearance result before time of the histologic and lesion sample within the time frame determines the HPV clearance endpoint.

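### The Week 36 efficacy window has a start but no end, so a subject without Week 36 tissue can be classified for the primary endpoint from a Week 64 biopsy

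*SAP*

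**What the plan says.** The primary objective (SAP section 1.1.5.1) concerns three doses: "The primary objective is to determine the efficacy of 3 doses of VGX-3100". The endpoint in section 4.3.1 is tied to a visit: histologic regression together with "virologic clearance of HPV-16/18 in intra-anal and/or peri-anal lesion tissue at Week 36".

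The sampling rule stands in two places:

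- Section 3.11, for histologic regression and virologic clearance in general: "any time starting from 14 days before the protocol-specified visit week".
- The note to Table 2, for the primary endpoint: "The efficacy time frame is defined by samples obtained any time starting from 14 days before the protocol-specified target date of Week 36". It continues: "The first such sample determines the histology endpoint". For virology: "The most recent HPV clearance result before time of the histologic and lesion sample within the time frame determines the HPV clearance endpoint".

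On what can happen after Week 36, section 1.2.1 says: "For partial responders at Week 36, a fourth dose may be administered at Week 40". Table 1 schedules post-baseline biopsies at Weeks 36 and 64 and gives the Week 36 visit a tolerance of plus or minus 1 week. Section 3.8 and section 4.3.2 split the later endpoints by three versus four doses.

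**The concern.** Both statements of the window fix its opening and leave it open afterwards. The tolerance in Table 1 governs when visits are scheduled, and neither statement uses it to close the efficacy window. Section 3.10 covers only adverse event and medication dates, and Table 2 has no entry for a subject without tissue. The open window is therefore the only rule that reaches a subject who missed the Week 36 biopsy, and it fills the gap with whatever tissue comes next.

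That tissue can lie well outside the time point the endpoint names, and a fourth dose can fall before it. The SAP treats the difference between three and four doses as worth stratifying at Weeks 64 and 88, yet nothing in the window rule keeps tissue taken after a fourth dose out of the Week 36 result. One specimen could also count at both Week 36 and Week 64. Because section 3.11 is general, the Week 36 secondary endpoints inherit the same open end. At stake is what the trial's only formal test measures.

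**Working it through.** **1. Timing (Table 1, sections 1.2.1 and 3.11).**
- The window opens 36 × 7 − 14 = 238 days after first dose, that is at Week 34.
- Week 36 to the next scheduled biopsy: 64 − 36 = 28 weeks.
- Possible fourth dose to that biopsy: 64 − 40 = 24 weeks.

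**2. Whom the rule touches.**
- Biopsied at Week 36: that sample comes first and decides. Later tissue is irrelevant.
- No Week 36 tissue, biopsied later: the later tissue decides the Week 36 endpoint.
- No Week 36 tissue and none later: the SAP does not say how the subject is classified.

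Only the second group is misplaced in time. Its size is not given. Section 3.1 assumes 90% evaluable at Week 36: 24 × 0.9 = 21.6, leaving 2 to 3 subjects. Section 3.9 uses the same 10% for subjects who discontinue before the Week 36 procedures, and they would not normally return for a Week 64 biopsy. So 2 to 3 is an upper guide.

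**3. The plan's power figure.** Inputs: 40% versus 15% (section 3.1), one-sided 0.05 (section 3.2), exact binomial test (section 4.3.1). The threshold r is the smallest count with P(X ≥ r | n, 0.15) = Σ C(n, j) 0.15^j 0.85^(n−j), j = r to n, below 0.05. Power is P(X ≥ r | n, 0.40).
- n = 21 (21.6 rounded down): r = 7, size 0.0287, power 0.7998.
- n = 22: r = 7, size 0.0368, power 0.8416.
- n = 24: r = 8, size 0.0199, power 0.8081.

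The stated value of about 80% reproduces at n = 21 and at n = 24.

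**4. What one subject can do (denominator 24).** Success needs p < 0.05 and a one-sided 95% lower limit above 0.15.
- 7/24: p = 0.0572, lower limit 0.146. Not superior.
- 8/24: p = 0.0199, lower limit 0.178. Superior.

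**5. The error runs in both directions.** Suppose two subjects lack Week 36 tissue and would otherwise be left out: 7/22 gives p = 0.0368, lower limit 0.160, a success. If both are biopsied late and are non-responders, the result becomes 7/24, p = 0.0572, a failure.

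**6. False-positive rate.** Let m subjects be classified from late tissue with response probability q, and the other 24 − m have a true Week 36 rate of 15%, with threshold 8 of 24. The chance of declaring superiority is P(A + B ≥ 8), with A ~ Bin(24 − m, 0.15) and B ~ Bin(m, q). The values of q are assumptions; the SAP gives none.

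| m | q = 15% | q = 25% | q = 40% | q = 50% |
|---|---|---|---|---|
| 1 | 0.0199 | 0.0230 | 0.0276 | 0.0308 |
| 2 | 0.0199 | 0.0265 | 0.0378 | 0.0463 |
| 3 | 0.0199 | 0.0304 | 0.0507 | 0.0675 |

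Over this range, 0.05 is passed only with three late subjects and a late response rate of about 40% or more.

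**7. Power if subjects without in-window tissue count as non-responders (threshold 8 of 24).** P(X ≥ 8 | 24 − m, 0.40):
- m = 2: 0.7102.
- m = 3: 0.6505.

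**The case against.** The best defence is that the first-sample rule already protects nearly everyone. Anyone biopsied at Week 36 is classified from that biopsy, and many of those without one will have left the study. This stands, and it limits how often the gap matters. It does not close the gap.

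Three stronger readings are tempting and are not supported:

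- *That 2 to 3 of 24 subjects will be classified late.* The 10% covers all who are not evaluable, including dropouts. The SAP gives no number for those who miss Week 36 tissue and come back.
- *That a fourth-dose effect will be credited to the primary endpoint as a matter of course.* The fourth dose is for subjects judged partial responders at Week 36. The case needs a subject assessed then, not biopsied then, dosed at Week 40 and biopsied at Week 64. It is conceivable, because the secondary objective describes partial response by lesion number and size as well as Investigator judgment, but it is likely rare. A note to Table 1 also appears to link the Week 64 biopsy to Subgroup C, which this SAP does not define.
- *That the open window favours the product.* Late tissue can also show HSIL or HPV, and non-study curative treatment already makes a non-responder under Table 2. In steps 5 and 6 above the effect runs both ways, and error inflation is modest unless several late subjects respond often.

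It is also true that one subject matters near the threshold of any exact test with 24 subjects. That is a reason to fix classification rules beforehand. Finally, a reader might infer that the SAP means missing Week 36 outcomes to count as non-response. It does not say so; that is a separate choice.

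**Conclusion.** The point holds in limited form. As written, the SAP can assign a Week 36 three-dose primary outcome from tissue taken about 28 weeks after the target, occasionally after a fourth dose, and can use the same specimen at Week 64. This conflicts with the endpoint's own time point and, in the rare fourth-dose case, with the dose count in the objective. No other section of the SAP corrects it.

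The number affected is unknown and probably small, and the direction is not fixed. The consequence can still be decisive, since the conclusion changes between 7 and 8 responders of 24. That contrast assumes all 24 mITT subjects are in the denominator, and the false-positive figures rest on assumed late response rates. The design power of about 80% is not in question.

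**What to change.** - In section 3.11 and the Table 2 note, close the Week 36 window at a stated date around the Week 36 visit, and in any case before any fourth dose. As one example, 14 days after the target would mirror the opening: it ends at Week 38, and the earliest Week 40 visit within tolerance is Week 39.
- Give the Week 64 window a similarly bounded end. Running it up to Week 88 would leave it open for 88 − 64 = 24 weeks, which is little better.
- Use tissue from outside the closed window only in a sensitivity analysis.
- State how mITT subjects with no in-window specimen are classified.

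No new rule is needed for several lesions in one window, because Table 2 already makes any HSIL or positive PCR in qualifying or new lesions a non-response.

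The cost is a few sentences and a programming rule, settled before database lock. Closing the window alone leaves the design power at about 80% if only subjects with in-window tissue are analysed (79.98% at n = 21). If subjects without such tissue count as non-responders over 24, power is about 71% with 2 missing or 65% with 3, and the SAP should say so.

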3.12. Interim Analyses

For reasons of futility (early evidence of poor efficacy of VGX-3100) or safety issues, the DSMB could recommend stopping enrollment at any time. However, no formal interim analyses will be performed for this study, and the study is not designed to be stopped early based on evidence of efficacy

4. STUDY ANALYSES

4.1. Subject Disposition

Subject disposition will be tabulated and include the number screened, the number treated in total, the number treated by the highest number of doses received, the number in each subject population for analysis, the number that completed all study treatments and follow-up visit, and the number who withdrew before completing the study and reason(s) for withdrawal. Reasons for not participating in study will also be summarized.

A by-subject data listing of study completion information including the reason for premature study withdrawal, if applicable, will be presented. Eligibility based on the inclusion /exclusion criteria and inclusion in the study populations will also be provided in listings.

4.2. Demographics and Baseline Characteristics

Demographics, baseline characteristics, and medical history will be summarized and presented. Age, height, weight, and BMI will be summarized using descriptive statistics (number of subjects, mean, SD, median, minimum, and maximum). The number and percentage of subjects in each ethnicity and race category also will be presented. Results at Screening for anal or anal/peri-anal HSIL category, HPV type, years of education, and type of insurance will also be presented.

Abnormal medical history will be summarized by term as collected on the electronic electronic case report form. Prior anal disease, HPV diagnoses, and reproductive history will be presented in data listings as well as tobacco history and alcohol use.

Data for each subject will also be provided in data listings.

4.3. Efficacy Evaluation

Efficacy analyses will be conducted using the mITT population. Supportive analyses of efficacy will be based on the PP population.

4.3.1. Primary Efficacy Endpoint

The primary endpoint is the combined response outcome of histologic regression of anal or anal/perianal HSIL and virologic clearance of HPV-16/18 in intra-anal and/or peri-anal lesion tissue at Week 36. Histologic regression is defined as no evidence of anal or anal/peri-anal HSIL on histology. Virologic clearance is defined as no evidence of HPV-16 and/or HPV-18 from intra-anal and/or peri-anal tissue by type-specific HPV testing. A treatment responder is defined as a subject with no histologic evidence of anal or anal/peri-anal HSIL and no evidence of HPV-16 or HPV-18 in anal lesion tissue and who did not receive any non-study treatment of curative intent of intra-anal and/or peri-anal lesions. A treatment non-responder is defined as a subject with histologic evidence of anal or anal/peri-anal HSIL, adenocarcinoma-in-situ, or anal or anal/peri-anal carcinoma, a subject with evidence of HPV-16/18 in anal lesion tissue, or a subject who received non-study treatment of curative intent of intra-anal and/or peri-anal lesions.

Table 2: Definition of Responder and Non-Responder for Primary Endpoint

Responder	Non-Responder

 • No histologic evidence of anal or anal/peri-anal HSIL in qualifying or new lesions AND • Negative PCR for HPV-16 or HPV-18 in anal lesion tissue in qualifying or new lesions AND • No non-study treatment of curative intent of intra-anal and/or peri-anal lesions 	
 • Histologic evidence of anal or anal/peri-anal HSIL, anal adenocarcinoma-in-situ, anal or anal/peri-anal carcinoma in qualifying or new lesions OR • PCR positive for HPV-16 or HPV-18 in anal lesion tissue in qualifying or new lesions OR • Any non-study treatment of curative intent of intra-anal and/or peri-anal lesions

Note: The efficacy time frame is defined by samples obtained any time starting from 14 days before the protocol-specified target date of Week 36. The first such sample determines the histology endpoint. The most recent HPV clearance result before time of the histologic and lesion sample within the time frame determines the HPV clearance endpoint.

The number and percentage of subjects with response for the primary endpoint will be presented and compared to historical control. A 1-sided p-value and corresponding 1-sided 95% CI using Clopper-Pearson exact binomial methods will be presented to prove superiority over historical control. Superiority of VGX-3100 will be declared if the 1-sided p-value is <0.05 and the lower end of the CI is greater than 0.15. Primary efficacy will be analyzed separately based on qualifying lesions present at baseline and for all lesions regardless of presence at baseline.

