5. Negative spot urine pregnancy test is required for female subjects at Screening, before each study treatment, high-resolution anoscopy (HRA), and biopsy/surgical excision; the pregnancy test at Week 40 would only be needed for subjects who receive an additional dose.
6. At least 34 mL (4 x 8.5-mL yellow [ACD] tubes) whole blood and 4 mL serum per time point. At least 68 mL whole blood and 8 mL serum should be collected before first dose.
7. At least 51 mL (6 x 8.5-mL yellow [ACD] tubes) whole blood and 4 mL serum should be collected at Week 15.
8. Digital Anal Rectal Examinations (DARE) are to be performed once cytology has been collected and before HRA.
9. An additional visit may be scheduled to perform HRA if worsening of disease is suspected. Biopsies should not be performed at any visit other than at entry (Screening) and Weeks 36 and 64 for Subgroup C unless the Investigator suspects invasive cancer. All biopsy samples and/or excision samples must be sent to the Pathology Adjudication Committee (PAC) for review.
10. Photography of qualifying lesion(s) must be performed before and after biopsy, and at all HRA examinations. If a pre-biopsy digital photograph is not available for a historical biopsy sample at Screening, a post-biopsy photo will be sufficient. Photographs of intra-anal lesion(s) will be for documentation purposes only. All qualifying peri-anal lesion(s) will be assessed using the ruler provided. The ruler should be placed in the field of vision and should be documented with photography at Screening, Day 0, and Weeks 4, 15, 28, 36, 64, and 88.
11. Tissue specimens (paraffin blocks) from all excised tissue lesion(s) that led to eligibility at study entry must be reviewed by the PAC, and residual tissue from entry and Weeks 36 and 64 specimen(s) (paraffin blocks) must be sent to the central laboratory for immune analysis and Human Papillomavirus (HPV) testing.
12. Potential dosing at Week 40 is applicable for partial responders only.
13. A phone call will be used to review the Participant Diary Card (PDC) with subjects within 8-14 days after doses 1 and 2. The subject will be expected to bring the PDC to the next visits for review. Subjects who receive an additional fourth dose will also have a phone call 8-14 days post dose 4 where the PDC will be reviewed. The subject should bring the PDC to the next visit.

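### The Table 2 note on the first sample conflicts with the lesion-level rule in the table itself, and the SAP does not say which decides Week 36 histology

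*SAP*

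**What the plan says.** Section 4.3.1 gives three statements that bear on Week 36 histology.

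- **Table 2, body.** The responder column requires "No histologic evidence of anal or anal/peri-anal HSIL in qualifying or new lesions". The non-responder column is triggered by "Histologic evidence of anal or anal/peri-anal HSIL, anal adenocarcinoma-in-situ, anal or anal/peri-anal carcinoma in qualifying or new lesions". Both refer to lesions in the plural.
- **Table 2, note.** "The efficacy time frame is defined by samples obtained any time starting from 14 days before the protocol-specified target date of Week 36". Then: "The first such sample determines the histology endpoint". The next sentence ties the HPV result to the time of that histologic sample.
- **Text after the table.** "Primary efficacy will be analyzed separately based on qualifying lesions present at baseline and for all lesions regardless of presence at baseline".

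Section 3.11 repeats the opening of the time frame, which "is defined as any time starting from 14 days before the protocol-specified visit week", and gives no end. Table 1 in Section 1.2.4 schedules the Week 36 visit at plus or minus 1 week. Footnote 9 to that table says "Biopsies should not be performed at any visit other than at entry (Screening) and Weeks 36 and 64" (the last for Subgroup C), with an exception when the investigator suspects invasive cancer. It also says "An additional visit may be scheduled to perform HRA if worsening of disease is suspected".

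**The concern.** Response is a statement about the subject, across lesions. The SAP expects several lesions in some subjects: Section 1.2.1 has all lesions of at least 4 mm biopsied at Screening, and Section 1.2.5.1 has an endpoint on the percent reduction in the number of qualifying lesions. The note is the only sentence that tells a programmer which histology record to use at Week 36. It speaks of one sample and has no rule for several lesions or for several dates.

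If the note is programmed as written, HSIL in a lesion sampled after the first one does not enter the primary endpoint. If the table body is programmed, it does. The trial is open-label with a single primary endpoint, so the choice should not be left until the data have been seen.

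**Working it through.** **1. The texts side by side.** The word *sample* in the note can mean one lesion's biopsy or all biopsies of the first sampling occasion. Both readings are shown.

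| Record | Note, *sample* = one biopsy | Note, *sample* = first occasion | Table 2 body |
|---|---|---|---|
| A. All lesions biopsied on one day, one shows HSIL | undefined: no biopsy is first | HSIL | non-responder |
| B. Two lesions sampled on different dates at Week 36; first without HSIL, second with HSIL | no HSIL | no HSIL | non-responder |
| C. For-cause biopsy of one lesion in the 14 days before Week 36, without HSIL; scheduled Week 36 biopsy of another lesion shows HSIL | no HSIL | no HSIL | non-responder |

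Reading *sample* as the occasion resolves A. It leaves B and C in conflict.

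**2. Direction.** The first sample is a subset of all samples in the window. The worst diagnosis in a subset cannot be worse than the worst diagnosis overall. Where the two rules differ, the note is therefore always the more favourable one for histology.

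**3. Window.** It opens 14 days before the Week 36 target date, while the visit may start 7 days before it. So 14 − 7 = 7 days of the window precede the earliest scheduled visit. If the visit takes place at the late end, 14 + 7 = 21 days precede it. A for-cause biopsy in that time becomes the first sample. There is no upper limit, so only the word *first* keeps Week 64 biopsies out, and it does so only for subjects who have an earlier sample.

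**4. The plan's power figure.** The inputs are 24 subjects, 15% against 40%, 90% evaluable (Section 3.1) and one-sided 0.05 (Section 3.2). The test is exact binomial: find the smallest r with P(X ≥ r | n, 0.15) < 0.05; power is then P(X ≥ r | n, 0.40).

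- 24 × 0.9 = 21.6; with n = 21, r = 7, error 0.029, power 0.800.
- With n = 24, r = 8, error 0.020, power 0.808.

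The stated value of about 80% reproduces. The present point does not affect it.

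**5. Success boundary at n = 24.** P(X ≥ r) is the sum over k from r to 24 of C(24, k) × 0.15^k × 0.85^(24−k). The lower limit is the one-sided 95% Clopper-Pearson limit.

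| Responders | p | Lower limit | Superiority declared |
|---|---|---|---|
| 7 | 0.057 | 0.146 | no |
| 8 | 0.020 | 0.178 | yes |

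One subject is 1/24 = 4.2 percentage points.

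**6. Sensitivity, by assumption only.** Let m be the share of true non-responders counted as responders when the true rate is 15%. The apparent rate is 0.15 + 0.85m. The expected number affected is 24 × 0.85 × m = 20.4m.

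| m | Subjects expected | Apparent rate | P(at least 8 of 24) |
|---|---|---|---|
| 0 | 0 | 15.0% | 0.020 |
| 2% | 0.4 | 16.7% | 0.036 |
| 5% | 1.0 | 19.3% | 0.074 |
| 10% | 2.0 | 23.5% | 0.183 |

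The SAP gives no value for m.

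**The case against.** The strongest reply is that the table body and the two required lesion analyses already show the intent. Neither analysis can be run from a single biopsy when a subject has several lesions. The coherent reading is then that the note picks the first sampling occasion and the table rows combine its lesions. The note also has a purpose: with an open-ended window, *first* keeps Week 64 biopsies out of the Week 36 endpoint. Footnote 9 confines biopsies to scheduled visits unless cancer is suspected, so most subjects will be sampled once.

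Much of this stands. A reader might infer that the SAP counts a subject with later-found HSIL as a responder. The documents do not support that, because the table body says the opposite and no order of precedence is given. Response also needs a negative PCR for HPV-16/18 in lesion tissue and no non-study treatment of curative intent, so missing the histology alone does not make a responder. (Read literally, the note ties the HPV result to the same first sample, so PCR from the later lesion may be left out too.) A reader might also take the sensitivity figures as an estimate of error inflation. They are not: the shares are assumed, and at 2% the error is still below 0.05. Nor does the SAP say that a non-diagnostic first specimen counts as absence of HSIL; that is a separate missing-data question.

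What the reply does not remove is records B and C, where even the sampling-occasion reading of the note contradicts the table.

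**Conclusion.** The SAP contains an unresolved conflict in the derivation of its only primary endpoint. The note, read literally, disregards HSIL in a lesion sampled on a later date at Week 36 and lets a for-cause biopsy of one lesion displace the scheduled set. The table body and the required lesion analyses do not. The window lacks a closing date.

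The number of subjects affected is probably small and cannot be derived from the SAP. The effect is possible rather than demonstrated: it needs a subject with discordant lesions sampled on different dates who also meets the other response criteria. Any disagreement on histology favours response, and at 24 subjects the distance between failure and success is one responder. That any single classification can matter at this sample size is not specific to this note, but it is reason enough to settle the rule before database lock.

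**What to change.** Replace the sentence on the first sample with an analysis rule along these lines:

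*Histology at Week 36 is the worst PAC diagnosis across all lesions sampled within the Week 36 window, which opens 14 days before the target date and closes on [stated date]. It is derived separately for qualifying lesions and for all lesions. An unscheduled biopsy of a single lesion within the window is added to the scheduled Week 36 biopsies and does not replace them.*

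The closing date is essential. Without it, a worst-diagnosis rule would let Week 64 histology determine the Week 36 endpoint. The Week 64 visit may begin at Week 62 (64 − 2), so the date must fall before then. The same closing date belongs in Section 3.11. The sentence on the HPV result should be reworded to match, because it refers to a single histologic sample.

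This changes only the derivation, not when biopsies are taken. It uses data already collected and costs a few lines in the SAP and its programming specification. The downside is a slightly less favourable response rate if any discordant cases occur.

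### The primary endpoint requires HPV clearance in lesion tissue, but the Table 2 note takes the HPV result from before the biopsy, when no tissue result can exist inside the window

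*SAP*

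**What the plan says.** All references are to the SAP.

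- **Specimen.** Section 4.3.1 ties clearance to tissue: "Virologic clearance is defined as no evidence of HPV-16 and/or HPV-18 from intra-anal and/or peri-anal tissue by type-specific HPV testing". Both columns of Table 2 also refer to lesion tissue.
- **Window.** The note under Table 2 opens it two weeks early: "The efficacy time frame is defined by samples obtained any time starting from 14 days before the protocol-specified target date of Week 36". It gives no closing date.
- **Histology half.** "The first such sample determines the histology endpoint".
- **Virologic half.** "The most recent HPV clearance result before time of the histologic and lesion sample within the time frame determines the HPV clearance endpoint".
- **When tissue is taken.** Table 1, footnote 9 (Section 1.2.4): "Biopsies should not be performed at any visit other than at entry (Screening) and Weeks 36 and 64 for Subgroup C", with an exception for suspected invasive cancer.
- **Where the tissue HPV result comes from.** Under footnote 11, residual tissue from the entry, Week 36 and Week 64 specimens "must be sent to the central laboratory for immune analysis and Human Papillomavirus (HPV) testing".
- **Table 2, PCR lines.** Responder: "Negative PCR for HPV-16 or HPV-18 in anal lesion tissue in qualifying or new lesions". Non-responder: "PCR positive for HPV-16 or HPV-18 in anal lesion tissue in qualifying or new lesions".
- **Swab.** Section 1.2.5.1 lists clearance by intra-anal swab at Week 36 as a separate secondary endpoint.

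**The concern.** The two halves of the composite should come from one Week 36 biopsy: histology from the slide and HPV status from the residual tissue. The note instead gives each half its own selection rule, and the HPV rule looks backwards from the biopsy. Programmed as written, it excludes the one specimen on which the endpoint is defined. The programmer must then leave the component empty or choose a substitute. This is the only endpoint with a formal test (Section 3.2), so the choice bears directly on whether superiority over the 15% historical control is declared.

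**Working it through.** **1. Timing**

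- The window opens at Week 36 minus 14 days, which is Week 34.
- Scheduled tissue after Screening falls at Week 36 and, for Subgroup C, Week 64. The first tissue on or after Week 34 is therefore normally the Week 36 biopsy, and by rule it fixes histology.
- A qualifying tissue HPV result would have to be (a) from tissue, (b) from Week 34 onwards and (c) before the first tissue sample from Week 34 onwards. Conditions (b) and (c) exclude each other for tissue.
- A for-cause biopsy inside the window does not help, because it becomes the first sample itself. If the Week 36 biopsy is missed and a later one is used, the same logic applies.

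**2. What each reading of the note yields**

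| Reading | HPV result used | Does it measure the stated endpoint? |
|---|---|---|
| Literal, tissue only | None | No; the component is empty |
| Window applied only to the lesion sample | Last earlier tissue, normally Screening | No; positive for HPV-16 and/or -18 by eligibility (Section 1.2.1), so essentially no responders |
| Any anal specimen in the window | Week 36 swab | No; separate secondary endpoint |
| *Before* read as *at or before* | Same biopsy | Yes, but the note does not say this |

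That the Week 36 swab precedes the biopsy is inferred from footnote 8, which puts cytology before the digital examination and anoscopy.

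**3. The plan's own figure**

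Inputs: 24 subjects, 90% evaluable, 40% against 15% (Section 3.1); one-sided 0.05 (Section 3.2); exact binomial test (Section 4.3.1). 24 × 0.9 = 21.6, rounded down to 21.

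- The smallest r with P(X ≥ r | 21, 0.15) < 0.05 is r = 7, where the probability is 0.0287.
- Power is P(X ≥ 7 | 21, 0.40) = 0.7998.
- With n = 24, r = 8: alpha 0.0199, power 0.8081.

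The stated power of about 80% is reproduced. Taking HPV status from the same biopsy alters none of these inputs.

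**4. What the workarounds could do (n = 21, r = 7)**

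- Empty component counted as non-response (an assumption): the response probability is 0, so power is 0.
- Screening tissue: essentially 0 responders, with the same result.
- Swab: the SAP gives no swab-tissue agreement, so these shifts are assumptions. If swabs miss virus present in tissue and the null rate rises from 15% to 17%, 20% or 25%, type I error is 0.053, 0.109 or 0.256. If swabs pick up virus from elsewhere and the true rate falls from 40% to 35% or 30%, power is 0.64 or 0.45.

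**5. The *or* in Table 2, read literally**

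| Tissue PCR | Responder line met | Non-responder line met |
|---|---|---|
| 16 negative, 18 negative | Yes | No |
| 16 positive, 18 negative | Yes | Yes |
| 16 negative, 18 positive | Yes | Yes |
| 16 positive, 18 positive | No | Yes |

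The middle rows overlap. Requiring both types to be negative turns their responder entries to No, and the two columns then separate cleanly.

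**The case against.** The best defence is that *before* was meant as *at or before*. Section 4.3.1 names lesion tissue throughout, and footnote 11 sends the Week 36 tissue for HPV testing, so the intended analysis can be recovered. As an account of intent this is probably right. It is not what the note says, and separate selection rules for the two halves would be unnecessary if one specimen was meant to supply both.

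Three stronger readings go further than the document allows:

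- *The primary endpoint will be taken from swabs.* The SAP nowhere directs this and its tissue definition points the other way. The swab is one possible workaround, and the error rates in step 4 rest on assumed disagreement.
- *All 24 subjects will be misclassified.* The sentence applies to all of them. How many would be classified wrongly depends on the reading adopted.
- *Single-type infections will be counted as cleared.* That would mean ignoring the non-responder column and the responder prose in the same section, which excludes evidence of either type. The *or* is a wording fault, secondary to the timing rule.

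**Conclusion.** The rule is wrong as written and should be corrected before the primary analysis is programmed. No literal reading of the note gives HPV clearance in Week 36 lesion tissue: it yields no qualifying result, and the available substitutes measure something else. The conclusion rests on the biopsy restriction in footnote 9 and on the histology sample being the first in the window; it needs no assumption about swab performance. The document itself supports no numerical bias. The only fixed quantities are that the rule governs the single tested endpoint in all 24 planned subjects and that the stated power of about 80% is unaffected by the correction. The overlap in Table 2 is a lesser point, because the surrounding text shows what was meant.

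**What to change.** Replace the last sentence of the Table 2 note with:

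> The type-specific HPV-16/18 PCR result from the same tissue specimen(s) that determine the histology endpoint determines the HPV clearance endpoint; swab results do not substitute.

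As a secondary repair, make Table 2's responder line require a negative PCR for both HPV-16 and HPV-18. Leave the rest of the line unchanged, including its reference to qualifying or new lesions. Demanding negativity in every sampled lesion would conflict with the end of Section 4.3.1, which analyses the primary endpoint separately for lesions present at baseline and for all lesions.

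If the protocol does not already say how a subject with no tissue HPV result is classified, add that here; Section 3.10 covers only adverse event and medication dates.

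The cost is two edits to the SAP. Week 36 tissue already goes for HPV testing, so no new samples are needed, and neither the sample size nor the success rule changes.
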